7.8 SAFETY ANALYSIS

All safety analyses will be performed on the treated set (TS). Treated patients will be analyzed according to their initial treatment.

Analyses will be performed as defined in Section 7.3.3 of the CTP. In general, safety analyses will be descriptive in nature and will be based on BI standards. No hypothesis testing is planned.

Safety data recorded during the Residual Effect Period (REP) of 30 days will be considered as on-treatment.

7.8.1 Adverse Events

The analyses of AEs will be descriptive in nature. All analyses will be based on the number of patients with AEs and not on the number of AEs. The analysis will be based on current BI standards ([5](#)). AEs will be coded using the most recent version of MedDRA. The severity of

AEs was assessed according to the Common Terminology Criteria for Adverse Events (CTCAE) Version 5.0. AEs will be analyzed as reported by the investigator and pooled independent of CTCAE version used if applicable.

For analysis multiple AE occurrence data on the CRF will be collapsed into an AE provided that all of the following applies:

- All AE attributes are identical (Low Level term (LLT), severity, action taken, therapy required, seriousness, reason for seriousness, relationship, outcome, AE of special interest (AESI)).
- The occurrences were time-overlapping or time-adjacent (time-adjacency of 2 occurrences is given if the second occurrence started on the same day or on the day after the end of the first occurrence).

Unless otherwise specified, the analyses of AEs will be based on the concept of treatment-emergent AEs, where a treatment-emergent AE has an onset in the analysing treatment period. For a definition of treatment refer to [Section 6.1](#). The AE analysis will be based on the on-treatment period which starts with the date of the first administration of study medication and ends 30 days after the last administration of study medication. AEs with an onset date in the screening period (time between informed consent date and date of the first administration of study medication) or follow-up period (time after the on-treatment period) will be listed separately.

AEs will be reported with start day and end day as calculated from the first day of treatment with study medication. For listings displaying AEs during the screening or follow-up period, the start and stop day are calculated from the start of the respective analysis period.

An overall summary of AEs will be presented.

Adverse events will be displayed by the initial dose of study medication administered on the first day of treatment.

The frequency of patients with adverse events during on-treatment period will be summarised by treatment, primary system organ class (SOC) and preferred term (PT), and will be sorted by the highest CTCAE grade. Separate tables will be provided for patients with:

- AEs by highest CTCAE grade
- Serious AEs (SAEs) by highest CTCAE grade
- Investigator assessed drug-related AEs by highest CTCAE grade
- Investigator assessed drug-related SAEs by highest CTCAE grade
- Investigator assessed AEs of special interest (AESIs) by highest CTCAE grade
- irAEs through the whole trial (i.e. including irAEs occurring after residual effect period) by highest CTCAE grade
- Investigator assessed infusion-related AEs by highest CTCAE grade
- AEs leading to treatment discontinuation by highest CTCAE grade

- AEs leading to death

For the definition of irAEs and AESIs refer to the CTP Section 5.2.6.1

The SOC will be sorted by frequency, and preferred terms will be sorted by frequency (within SOC).

Adverse events that are immune mediated can potentially begin more than 30 days after treatment. Additional tables will summarize all immune related events, including events with onset more than 30 days after the last treatment.

AEs leading to death during the on-treatment period will be tabulated by SOC and PT. Reported fatal AEs during follow-up period will be listed. All deaths during the study will be summarized by primary cause of death (death due to disease, death due to AE, death cause unknown, other).

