7.3.3 Safety analyses

Adverse events will be coded using the Medical Dictionary for Drug Regulatory Activities (MedDRA). Standard BI summary tables and listings will be produced. All adverse events with an onset between start of treatment (i.e. 1st administration of anti-PD-1 treatment BI 754091 at Cycle1 Day1) and the safety follow-up (FU) 30 days after the last dose of trial medications, will be assigned to the on-treatment period for evaluation. Statistical analysis and reporting of adverse events will concentrate on treatment-emergent adverse events, i.e. all adverse events occurring between start of treatment and end of the residual effect period. Adverse events that start before first drug intake and deteriorate under treatment will also be considered as 'treatment-emergent'.

All treated patients will be included in the safety analysis. In general, safety analyses will be descriptive in nature and will be based on BI standards. No hypothesis testing is planned.

Frequency, severity, and causal relationship of adverse events will be tabulated by system organ class and preferred term after coding according to the current version of MedDRA at the database lock.

Laboratory data will be analysed both quantitatively as well as qualitatively. The latter will be done via comparison of laboratory data to their reference ranges. Values outside the reference range as well as values defined as clinically relevant will be summarised. Treatment groups will be compared descriptively with regard to distribution parameters as well as with regard to frequency and percentage of patients with abnormal values or clinically relevant abnormal values.

Vital signs, physical examinations, or other safety-relevant data observed at screening, baseline, during the course of the trial and at the end-of-trial evaluation will be assessed with regard to possible changes compared to findings before start of treatment.

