6. GENERAL ANALYSIS DEFINITIONS

6.1 TREATMENT(S)

In this Phase I trial treatments are not randomised.

Patients will receive combination treatment of BI 754111 (600 mg) and ezabenlimab (240 mg). Data of study parts 1 and 2 will be reported together, grouped by (cold) blocking dose of BI 754111 (cohorts).

Table 6.1: 1 Definition of analysing treatment periods for safety analysis

Analysing Treatment Period	Start Date	Stop Date
Screening	Date of informed consent	Date/Time of the first administration of trial medication
On-treatment	Date/Time of the first administration of trial treatment	Date of the last administration of trial medication + 30 days (residual effect period)
Follow-up	Date of the last administration of trial treatment + 31 days	Date of the last per protocol visit

Note: a 30-day safety follow-up period is defined for this trial.

For safety analyses, adverse events (AEs) will be classified to one of the following time periods: “Screening”, “On-Treatment” or “Follow-up”. This will be applied for all adverse events. Detailed rule for assigning AEs to these time periods are listed below:

- If the date of informed consent \leq AE onset date $<$ date/time of first administration of [⁸⁹Zr]Zr-BI 754111, ezabenlimab or BI 754111, then the AE is assigned to “Screening”;
- If date/time of first administration of ezabenlimab or BI 754111 \leq AE onset date \leq date of last administration of [⁸⁹Zr]Zr-BI 754111, ezabenlimab or BI 754111 + 30 days, then the AE is assigned to “On-Treatment”;
- If AE onset date $>$ date of last administration of [⁸⁹Zr]Zr-BI 754111, ezabenlimab or BI 754111 + 30 days, then the AE is assigned to “Follow-up”

For the on-treatment period, the nominal trial medication assigned at the beginning of the first treatment cycle (Cycle 3) will be used as label of the analysing treatment. In cases where patients stop treatment before Cycle 3, the actual treatment doses applied in Cycles 1 and 2 will be used as label. Tables for the on-treatment period will contain a “total” column, representing all doses of trial medication combined.

The first treatment cycle starts with the first administration of any trial medication and lasts for 21 days. Treatment cycles generally consist of 21 days.

Adverse Events (AEs) that have onset date during the Screening or Follow-Up periods will be displayed in separate listings from those occurred during the on-treatment period. Listings of AEs will not present a “total” category.

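### The SAP classifies adverse events by onset date alone, contradicting the protocol's rule, and its own cross-reference to it, that events worsening on treatment are treatment-emergent

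*SAP*

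**What the plan says.** **Protocol 7.3.3** bases the safety analysis on treatment-emergent events, defined as "all adverse events occurring between start of treatment and end of the residual effect period". It then widens the definition: "Adverse events that start before first drug intake and deteriorate under treatment will also be considered as" treatment-emergent.

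**SAP 6.1** sorts events into Screening, On-Treatment and Follow-up by comparing the onset date with the dosing dates. It says of this classification: "This will be applied for all adverse events". It continues: "Adverse Events (AEs) that have onset date during the Screening or Follow-Up periods will be displayed in separate listings".

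**SAP 7.8.1** bases the analyses on the treatment-emergent concept, under which "a treatment-emergent AE has an onset in the analysing treatment period". The group it lists separately includes "AEs with an onset date in the screening period (time between informed consent date and date of the first administration of study medication"). Neither SAP section makes an exception for later worsening.

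**SAP 7.8**, the parent section of 7.8.1, states that the safety analyses are those defined in protocol 7.3.3. **SAP 4** states that the analysis plan has not changed since protocol version 3.0. It names some analyses that will not be done, but no visible text there announces a narrower definition of treatment-emergent.

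**The concern.** The protocol's second sentence covers events already open at first dose. Such events can exist here. Protocol 5.2.6.2.1 collects adverse events from the signing of consent, and protocol 6.2.1 allows up to 15 days of screening before the first BI 754091 dose. Screening also includes a core needle biopsy unless contraindicated, and protocol 1.3 names pneumothorax and bleeding as complications of biopsy. An event of this kind could begin at low grade before dosing and become more severe afterwards.

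At stake is the completeness of the on-treatment safety tables. Any events lost this way are lost in one direction, toward lower rates and lower maximum grades. Two programmers working from the same SAP could also produce different tables, one following the 7.8 cross-reference and the other the 6.1 algorithm.

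**Working it through.** The plan states no figure to reproduce. The check compares the rules, traces an example through them, and then works out the weight of one patient.

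**1. The rules side by side**

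| Source | Event begins on treatment | Event begins before first dose and worsens on treatment |
|---|---|---|
| Protocol 7.3.3 | Treatment-emergent | Treatment-emergent |
| SAP 7.8 (by reference to protocol 7.3.3) | Treatment-emergent | Treatment-emergent |
| SAP 6.1 and 7.8.1 (detailed rules) | On-treatment | Screening, listed separately, if the event keeps its original onset |

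The sources agree in the first column and conflict only in the second.

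**2. An example traced through the rules.** Take an illustrative event of Grade 1 with onset on Day -5 that worsens to Grade 3 on Day 10.

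- *Protocol 7.3.3:* treatment-emergent.
- *SAP 6.1 and 7.8.1, one record with onset on Day -5:* assigned to Screening, listed separately and absent from the on-treatment frequency tables.
- *SAP 6.1 and 7.8.1, worsening entered as a second record with onset on Day 10:* that record is assigned to On-Treatment and tabulated. The collapsing rule in SAP 7.8.1 merges occurrences only when all attributes match, including severity, so the Grade 1 and Grade 3 records stay separate.

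The result therefore depends on how the worsening is recorded. Protocol 5.2.6.2.3 requires worsening of pre-existing conditions, other than the underlying disease, to be recorded as an adverse event. That should protect conditions that pre-date the trial. Neither document says how to date the worsening of an event already open from screening.

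**3. Tables affected in the single-record case.** From the list in SAP 7.8.1, these are overall incidence, highest CTCAE grade, serious events and drug-related events.

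**4. Weight of one patient.** One misclassified patient lowers an incidence by 100/N percentage points. The planned maximum in protocol 7.7 is 5 + 35 = 40, which gives 100/40 = 2.5 points. SAP 4 says the trial was terminated prematurely. If fewer than 40 were treated, the weight is larger, but the SAP does not give the actual N.

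**The case against.** **The protocol rule is still in force.** SAP 7.8 imports protocol 7.3.3, SAP 3 says the SAP is based on protocol Section 7, and the onset definition in 7.8.1 opens with a caveat for cases specified otherwise. Assigning periods by onset is also the protocol's own approach. This stands to the extent that a reader who infers that the SAP removed the worsening rule goes too far. The conflict remains, because a general reference sits beside specific, explicit rules that give a different answer, and nothing says which prevails.

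**Worsening may be recorded with its own onset.** This stands as a limit. A reader might infer that all worsening events leave the tables. The documents support that only for an event that starts between consent and first dose and is held as one record under its screening date. The sponsor's adverse event standard cited in SAP 7.8.1 may settle the recording question, but it is not part of the two documents. The protocol's worsening sentence would be largely unnecessary if every worsening always carried a new onset.

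**Other outputs would show much of it.** This stands in part. Affected events remain in listings. SAP 7.8.2 reports worst on-treatment laboratory grade and change from baseline grade, so rising liver enzymes would be visible. SAP 7.8.1 summarises all deaths by primary cause. Symptomatic events have no such second route into the tables.

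**The size could be exaggerated.** A reader might put a share on the patients affected, or quote 100/2 = 50 points for the two-patient minimum cohort in protocol 3.1. The documents support neither. They give no frequency of worsening screening events. They also leave the table columns unsettled: SAP 6.1 groups reporting by Cycle 2 blocking dose but labels on-treatment data by the Cycle 3 dose, which is common to patients who reach that cycle, and SAP 7.8.1 displays events by the first-day dose, which is BI 754091 240 mg for everyone.

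**Conclusion.** The point holds as a contradiction between SAP 6.1 and 7.8.1 on one side and protocol 7.3.3 and SAP 7.8 on the other, with no change declared in SAP 4. It should be corrected, because the detailed SAP rules, coded as written, would misclassify events that the protocol counts.

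The loss is conditional. It needs literal programming of the onset rules and a worsened event kept as one record with its screening onset. Where both apply, on-treatment rates and grades are understated. Each affected patient is worth 2.5 percentage points at N = 40, and more at a smaller N. The number of such patients cannot be derived from the documents.

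The safety analysis is descriptive and the SUV primary endpoint is untouched.

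**What to change.** In SAP 6.1 and 7.8.1, restate the protocol 7.3.3 rule: an adverse event with onset before first study medication that deteriorates during the on-treatment period is assigned to On-treatment, tabulated at the worsened grade and dated from the worsening. Define deterioration so that it can be programmed, for example as an increase in CTCAE grade. That threshold makes the protocol's wording operational. The protocol itself sets none, so the SAP should say that the choice is its own.

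The cost is a sentence in each section and a small programming rule. The date and grade of worsening must also be available in the data. Adverse event rates may come out slightly higher.

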7.8.2 Laboratory data

The analysis of laboratory data will be descriptive in nature and will be based on BI standards (6). The same on-treatment period as considered for the analysis of adverse events will be applied for laboratory values. Patients having at least one post-baseline laboratory value will be displayed in the descriptive analyses. Patients with missing CTCAE grade at baseline or no baseline value but with post-baseline values will be displayed in a new category “Missing CTCAE grade at baseline” for those laboratory parameters where CTCAE grading is applicable. CTCAE grades for applicable laboratory parameters will be calculated according to CTCAE Version 5.0.

The following outputs will be presented:

- Worst CTCAE grade experienced during the on-treatment phase
- Transitions of CTCAE grade from baseline to worst laboratory value

For lab tests for which CTCAE grades are not used for at least one direction of interest, frequency of patients with shifts from baseline as defined in the Project Safety Statistical Analysis Plan (SSAP (8)) will be followed.

Analysis

The Laboratory tests will be classified into the following categories:

- Primary- full analysis
- Secondary- listing of possible clinically significant values
- Diagnostic- listing of all observed values
- Not analyzed

The following outputs will be presented for primary laboratory tests:

- Descriptive statistics, including changes from baseline
- Frequency of patients with shifts from baseline
 - Shifts will be defined in terms of
 - CTCAE grades will be used for laboratory tests with CTCAE grades defined
 - The upper and lower reference limits will be used for laboratory tests without CTCAE grades
- Frequency of patients with possible clinically significant abnormalities

The analysis of secondary laboratory tests will be limited to tabulation of the frequency of patients with possible clinically significant abnormalities.

Possible clinically significant abnormal laboratory values:

[figure not shown]
Possible clinically significant abnormal laboratory values are defined as those laboratory values that are of CTCAE Grade ≥ 2 and show an increase from baseline value by at least one CTCAE grade. For those parameters for which no CTCAE grade has been defined, definition in SSAP (8) will be used to determine possible clinical significance. Frequency of patients with possible clinically significant abnormal laboratory values will be provided whenever applicable. If no baseline value is available but the patient has a post-baseline laboratory value of CTCAE Grade ≥ 2 an increase from baseline will be assumed, i.e. the laboratory value considered as possible clinically significant.

Laboratory tests classified as “diagnostic” are recorded as a follow-up to abnormalities of associated lab tests for diagnostic purposes i.e. amylase and lipase would be measured to investigate possible pancreatitis. These values will be presented in a separate listing. No other analyses will be performed.

Analyses of descriptive statistics should use normalized lab values.

Analyses of frequencies of patients with potential clinical significance, analyses of shift, and liver function categories tables should use converted values.

Baseline for safety laboratory parameters will be the last available measurement before the start of study drug. Laboratory measurements taken up to 30 days after the last administration of study drug will be considered as on-treatment.

Handling of CTCAE grade -1 and -9 laboratory parameters:

Generally, in case only one direction of worsening (high or low laboratory value) is specified in the CTCAE document, there is no need to examine the other direction. Therefore, for calculating the change in CTCAE grade, patients with a CTCAE grade of -9 (no CTCAE grade defined) will be automatically treated as CTCAE grade 0 for all analyses. In laboratory listings, the CTCAE grade will be displayed as -9.

There are certain parameters for which CTCAE grades can only be differentiated by taking physiological consequences into account. These laboratory values will be coded as -1. As these definitions aggregate laboratory data and adverse events or concomitant therapies no analyses based on CTCAE grades will be done. Instead standard laboratory analyses as for laboratory parameters without CTCAE grade definitions will be done.

Corrected calcium:

The grading of hypocalcemia is based on corrected calcium as calcium can be falsely low if hypoalbuminemia is present. The following corrective calculation will be performed:

$$\text{Corrected calcium (mg/dL)} = \text{Total Calcium (mg/dL)} - 0.8[\text{Albumin (g/dL)}-4]$$

No correction of the reference range has to be done. The reported reference range of total calcium will be used for analyses.

Corrected calcium can be only derived at a certain time point in case both laboratory values total calcium and albumin have been reported for the patient in the same laboratory sample.

Liver Function tests and potential Hy's Law

A listing of all liver function tests will be provided for all patients who meet the following criteria at any time:

- ALT or AST $\geq 3 \times \text{ULN}$ and elevation of total bilirubin $\geq 2 \times \text{ULN}$ at the same time

In addition, tables of liver function test abnormalities will be provided.

7.8.3 Vital signs

Only descriptive statistics are planned for this section of the report.

7.8.4 ECG

Patients with abnormal ECG data will be provided.

7.8.5 Others

Other parameters relevant for safety as height, weight, and ECOG score will be analyzed descriptively and displayed in patient listings.

ECOG

A shift table from worst, best and last ECOG performance status on treatment from baseline will be provided.

[REDACTED]

[figure not shown]
[REDACTED]

[REDACTED]

[REDACTED]

10. HISTORY TABLE

Table 10: 1 History table

Version	Date (DD-MMM-YY)	Author	Sections changed	Brief description of change
1	15-FEB-21		None	This is the final TSAP.
